2.1 Overview and study design

The Nudge microrandomized trial (MRT) will enroll 201 young adults and test whether providing daily intervention messages tailored to recent behavior and context and targeting one of 7 different behavior change techniques (BCTs), compared with not providing a message, increases subsequent achievement of 3 daily weight-related behavioral goals (self-weighing, active minutes, red food intake). Participants will receive a mobile-delivered behavioral weight loss program and be micro-randomized three times a day over a 6-month period (i.e., 504 randomizations per individual).

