2.2 Intervention Overview

All participants will receive a 6-month core intervention adapted from the Diabetes Prevention Program specially for young adults and to be delivered remotely via an automated program. The program, Nudge, will be delivered through a native smartphone app that includes weekly lessons, weekly tailored feedback, a native food log to track red foods, visual displays of behavioral progress, and in-app messages. All participants will receive a wireless scale and an activity tracker (Fitbit, San Francisco, CA) in the mail followed by an individual videochat session with an interventionist. For each of the 24 weeks of the program, at 3 scheduled time points per day, participants will be randomized to receive or not receive a BCT message promoting achievement of proximal weight management behaviors (weighing, activity, red food intake). Thus, participants will receive 0-3 messages per day. The primary outcome is same-day achievement of daily goals (weighing, active minutes goal, red food limit), evaluated among observations in which participants received a message compared to observations in which the participant did not receive a message.

Questions answered through Nudge MRT	

 Does providing a BCT message increase goal attainment on the same day it is delivered? (Aim 1) Do each of the BCT message types have different effects on goal attainment? (Aim 1) Do BCT messages' effects change over time? If so, what is the nature of the change (i.e., when does the effect disappear)? (Aim 2) Do BCT messages work differently when delivered under different contexts (e.g., time in program, time of day, previous dose of BCT messages, recent behaviors)? (Aim 3) 	
Intervention components to be tested across 3 behaviors: 7 behavior change techniques (BCT messages)	
1.4 Action planning	Message prompts detailed planning of performance of behavior via implementation intentions
1.6 Discrepancy between current behavior and goal	Message draws attention to discrepancies between a person's current behavior and previously set outcomes goals, behavioral goals, or action plans
2.7 Feedback on outcome of behavior	Message provides feedback on the outcome of performance of the behavior (i.e., weight)
3.1 Social support	Message advises on or provides social support for performance of the behavior
6.2 Social comparison	Message draws attention to others' performance to allow comparison with person's own performance

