3. STUDY PROCEDURES

Data Collection

Measures of the primary outcomes (daily weighing and achievement of active minutes goal and red food limit) will be collected daily throughout the study via self-monitoring tools (described below). All study participants will complete objective weight measurements and self-administered online surveys at baseline, 3 months, and 6 months post-intervention. Participants will also complete two dietary recalls at baseline and two dietary recalls at 6 months to measure average dietary intake. Participants will receive \$50, \$25, and \$75 for completing baseline, 3, and 6-month assessments, respectively. Online surveys will include measures of theoretical mediators, other psychosocial constructs, and process measures. We will send emails and texts prompting participants to complete assessments, with follow-up emails and phone calls to non-respondents, as necessary. Measures and timing are described below.

Measures

Primary Proximal Outcome Measures (collected daily)

Intervention messages are intended to promote achievement of 3 daily weight-related behavioral goals: weigh daily, meet a daily active minutes (AM) goal, and stay at or under a daily RF limit. Thus, the primary outcome is the achievement of behavioral goals on the day of randomization (i.e., until 12:00AM).

Met daily weighing goal. Weighing behavior will be objectively measured daily using a smart scale (Fitbit Aria Air, San Francisco, CA) at the participant's home. Participants will be instructed to weigh themselves daily on the scale in light clothing and without shoes. A dichotomous indicator of whether the participant weighed will be calculated.

Met daily active minutes (AM) goal. Participants will have a daily AM goal that may change or stay the same at the beginning of each program week. Fitbit trackers will be used to collect daily AM data, defined by

Fitbit as physical activity of at least moderate-to-vigorous intensity that is accumulated in 10-minute bouts. We will calculate a dichotomous outcome of whether a participant met their daily AM goal (days with no tracker wear are counted as not meeting the goal) on the day of randomization.

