4. STATISTICAL CONSIDERATIONS

Sample Size and Power

Our power analysis is based on a sample size calculator built in an R package (MRT-SS)⁵² for detecting proximal treatment effects in microrandomized trials developed by Liao et al,⁵³ expanding on more general results for sample size calculations for longitudinal trials from Tu et al.⁵⁴ Inputs to the sample size calculator are: desired alpha (.05), the number of outcome occasions ($T=168$ days for each proximal outcome), average probability of message availability each day, the randomization probability for a given message if it is available (0.5), and the standardized proximal treatment effect $\bar{d}_t = \sum_t d_t / T$ across all time points. Based on our prior research¹⁶ and the previous MRTs with published effects sizes,^{31,32,55} we assume that \bar{d}_t ranges from .03 to .15. Based on our previous studies with young adults^{56,57} and the pilot MRT,¹⁶ assuming 17% attrition by day 168, we estimated that a sample size of $N=201$ would be required to have an average of 150 usable days per person ($168 \text{ days} \times .83 + 84 \text{ days} \times .17 = 154$), for a total of 30,954 person-day observations ($N=201 \times 154$; i.e., over 4400 person-day observations per each of 7 BCT message interventions across 3 behaviors). This is consistent with a prior MRT that evaluated 6061 available decision points to test 2 different options for an intervention component (i.e., walking suggestions, anti-sedentary suggestions) among 37 participants.³² We will use all available data points in these analyses and test the sensitivity of our findings to dropout status by conducting completer-only and dropper-only analyses. The estimated minimum detectable standardized effect size with 80% power across the planned analyses ranges from .04 to .13.

Statistical Analysis Plan

Data analysis will be performed using R statistical software (version 4.0.3). Baseline demographic and descriptive characteristics will be summarized globally, using frequencies and percentages for categorical variables, and means and standard deviations (SD) for inherently quantitative variables. Prior to conducting data analyses, we will audit the data for completeness and quality, including missing data. We will evaluate response distributions to ensure that they meet assumptions of planned analyses (see below), including the detection of outliers.

Analysis of primary outcomes

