We will test: 1) whether any intervention message (versus no message) increases adherence to daily weight loss behaviors among young adults, 2) whether a behavior-specific message (versus not receiving the behavior-specific message) increases adherence to the respective behavioral goal, and 3) finally the unique effect of each BCT message for the three proximal outcomes. We will use generalized estimating equations (GEE) with an independence working residual correlation matrix to account for nesting of observations within individuals.⁵⁸ and use Benjamini-Hochberg-Storey correction for multiple testing.⁵⁹

Analysis of whether effects of BCT messages change over time

We will also examine whether the effects of BCT messages on daily adherence to weight loss behaviors change over time (week in program, time of day) and, if so, the nature of the change (e.g., when effects disappear). Thus, we will expand upon the model described above by: 1) including linear and quadratic main effects of time and interaction terms, between an indicator of day in the program and treatment assignment, to test whether the treatment effect changes over time.⁵⁸ We will examine differences in the average and estimated time trends in treatment effects of receiving a behavior-specific message, and then the unique effect of each BCT message for the three proximal outcomes.

Analysis of whether effects of BCT messages are moderated by participants' contextual factors

We will evaluate whether the causal effect of receiving a BCT message interacts with participants' contextual factors, including past behaviors and individual characteristics. We will use standard moderation analysis within the GEE framework for these analyses, which involves the inclusion of main effects and interaction terms. Significant moderation effects will be probed using simple slopes analysis to determine the conditional region and direction of significance. The primary moderators to be tested are participants' 7-day history of contextual factors at the time of randomization (achievement of weight-related behavioral goals, streaks and lapses in self-monitoring, weight change, previous BCT messages received). Exploratory time-invariant potential moderators include demographic and health characteristics (e.g., sex, age, baseline BMI).

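### The whole-day outcome includes behavior before the decision point, and the Aim 1 model does not adjust for goals already settled, which costs precision and clouds time-of-day results

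*Combined protocol and SAP*

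**What the plan says.** - **Outcome.** Section 3 (Primary Proximal Outcome Measures): "the primary outcome is the achievement of behavioral goals on the day of randomization (i.e., until 12:00AM". This fixes the end of the window. Nothing starts it at the decision point.
- **Question.** Section 2.1 asks whether a message, "compared with not providing a message, increases subsequent achievement of 3 daily weight-related behavioral goals". Section 2.2 puts the Aim 1 question as goal attainment on the day the message is delivered.
- **Decision points.** Section 2.2: "at 3 scheduled time points per day, participants will be randomized to receive or not receive a BCT message". Section 2.1 counts "i.e., 504 randomizations per individual". Clock times are not given.
- **Outcome occasions.** Section 4 (Sample Size and Power) uses "the number of outcome occasions ($T=168$ days for each proximal outcome", so three randomizations share each daily outcome. It also names "average probability of message availability each day" as an input, without a value or a rule.
- **Analysis.** Section 4 (Analysis of primary outcomes) specifies GEE with an independence working correlation. It names no covariate for the participant's status earlier that day and no link function. The primary moderators look back over seven days.
- **Time of day.** Section 4 says effects may "change over time (week in program, time of day", but the only interaction it writes out is between treatment and day in program.

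**The concern.** A weigh-in settles the weighing goal for the rest of the day. The active-minutes goal can likewise be reached, and the red-food limit exceeded, before a later decision point. (The red-food goal can be lost early but not secured early, because more red foods can still be logged.) At such a point a message cannot change that goal's same-day result. The point adds zero effect and keeps its share of the outcome variance.

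Two things are at stake. Aim 1 looks for small effects (section 4 gives detectable standardized effects of .04 to .13), so avoidable noise matters. Aim 2 asks about time of day, and section 2 says the findings will shape the next adaptive intervention. A difference between message slots could come from the message, from how many goals are already settled, or from how much of the day is left.

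**Working it through.** **1. The plan's own counts reproduce.** 24 × 7 × 3 = 504 randomizations. 168 × .83 + 84 × .17 = 153.72, rounded to 154 usable days. 201 × 154 = 30,954 person-days, and 30,954 / 7 = 4,422. The detectable range .04 to .13 cannot be checked, because it depends on the missing availability value. With 154 days, a constant effect and the standard micro-randomized-trial F-test, full availability gives .032, while .04 needs availability of about .64 and .13 needs about .06.

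**2. Dilution.** Let s be the share of decision points already settled for a goal. The effect there is zero, so

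whole-day effect = (1 - s) × effect among open points.

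Assumed example, 5 points among open points:
- s = .1/.3/.5 at the three points gives 4.5/3.5/2.5, average 3.5.
- s = .3/.6/.8 gives 3.5/2.0/1.0, average 2.2.

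**3. Efficiency from adjustment.** Let P be the share of days on which the goal is met and c the share already met before the point. The rate among open points is po = (P - c)/(1 - c). On the risk-difference scale the unadjusted outcome variance is P(1 - P). With the settled indicator in the model, the residual variance is (1 - c) × po × (1 - po). The variance ratio reduces to P(1 - c)/(P - c). With P = .6 (assumed), P(1 - P) = .24:

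| c | po | residual variance | ratio |
|---|---|---|---|
| .30 | .43 | .171 | .24/.171 = 1.4 |
| .45 | .27 | .109 | .24/.109 = 2.2 |
| .50 | .20 | .080 | .24/.080 = 3.0 |

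Analyzing only open points gives the same ratios, so nothing need be dropped to gain the precision. For a goal lost early, the same algebra gives (1 - P)(1 - c)/(1 - P - c). At P = .6 and c = .1 (assumed) this is .4 × .9/.3 = 1.2, so the red-food gain may be modest. These ratios are for one decision point and ignore within-person correlation. In an assumed three-point simulation with about 42% to 54% settled, adjustment cut the standard error from .0035 to .0019 and left the estimate at .0235.

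**4. Time of day.** Assume every message adds a 5-point push (for red foods, a 5-point cut in the chance of exceeding the limit) in the next interval only. Let h be the average chance that an open goal settles in an interval. The whole-day effect at a point is (1 - s) × 5 × the product of (1 - h) over the later intervals.
- Morning weighers, s = .50/.588/.639, later h = .125: .50 × 5 × .875 × .875 = 1.9; .412 × 5 × .875 = 1.8; .361 × 5 = 1.8 (simulated: 1.9/1.8/1.7).
- Even pattern, s = .20/.38/.52, h = .225: .80 × 5 × .775 × .775 = 2.4; .62 × 5 × .775 = 2.4; .48 × 5 = 2.4.
- Red foods lost mostly at dinner, s = .02/.074/.162, later h = .095 and .275: .98 × 5 × .905 × .725 = 3.2; .926 × 5 × .725 = 3.4; .838 × 5 = 4.2.

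The same push therefore gives a slightly falling, a flat and a rising pattern. With no true effect, the simulated whole-day differences were 0.0 at all three points.

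**The case against.** The strongest reply is that the plan answers its own question. Section 2.2 asks about same-day attainment. With randomization at 0.5 for an available message, the whole-day contrast is unbiased for that. A message sent after the goal is settled truly has no same-day effect on it, and averaging over such points describes the effect of sending at that scheduled time. **This stands.** A reader might infer that Aim 1 is biased or understates every effect. The documents do not support that: the open-point effect is a different, legitimate estimand.

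Second, messages are described as just-in-time and tailored to recent behavior, and an availability condition exists. It may already remove some settled goals for behavior-specific messages. **This stands in part.** The rule is not described, and nothing shows that it protects the any-message test, which is scored on all three goals.

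Third, restricting to open points brings its own composition effect. In step 3 the rate among open points falls from 43% at c = .30 to 20% at c = .50, so late open points are increasingly days unlikely to succeed. Whether a point is open can also depend on earlier same-day messages. **This stands**, and is why open points belong in a secondary analysis.

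Fourth, the next-day goal outcomes in section 3 exclude behavior earlier on the randomization day. True, but they are secondary.

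**Conclusion.** The point holds as one of precision and interpretation. Unless the undescribed availability rule removes settled points, the Aim 1 test carries avoidable noise, and its estimate is (1 - s) times the open-point effect. Both s and the clock times are absent from the documents, so every size here is assumed. The gain from adjustment is 1.4 to 3.0 times for weighing with 60% of days weighed and 30% to 50% settled. The top value supposes that .50/.60 = 83% of weigh-ins come before the decision point.

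Two stronger readings should be set aside. One is that the design builds in a false time-of-day pattern that would make late messages look useless. Step 4 shows no fixed direction and no false positive, and section 4 writes out no time-of-day interaction. The defensible statement is that such a pattern would mix message effect, settled share and time left. The other is that the trial is underpowered for this reason. Section 4 does not say whether its assumed effects of .03 to .15 are whole-day or open-point effects; if they are whole-day, the dilution is already in them.

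**What to change.** 1. State the availability rule, and whether a point is unavailable for a goal already settled.
2. In the Aim 1 GEE, keep all available decision points and the whole-day outcome. Add, for each goal, an indicator of settled status that day (weighed; active-minutes goal met; red-food limit exceeded), taken just before randomization and entered by decision point.
3. State the effect scale. Step 3 holds for risk differences. With a logit link, already-met points predict success perfectly, and the treatment coefficient would come from open points only. In that case, standardize back to a risk difference over all points.
4. Report the settled share by goal and decision point.
5. Give effects among open points as a secondary analysis, including by time of day for Aim 2, with the time-of-day term written out. Note that later open points are a selected set, can depend on earlier same-day messages, and have less of the day left.

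The cost is SAP wording and a derivation from time-stamped scale, tracker and food-log data. The documents do not promise event times, and sync can lag and food can be logged after it is eaten, so availability and delay must be confirmed first. Data that reached the server before randomization are the safest basis for the indicator. The sample size and the intervention do not change.

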- Evaluate the effects of each behavior change technique message (i.e., BCT message) on daily adherence to weight loss behaviors in a 6-month micro-randomized trial among young adults.
- Determine whether the effects of BCT messages on proximal outcomes change over time.
- Assess whether the effects of BCT messages on proximal outcomes are moderated by participants’ contextual factors.

Test Article(s)
(If Applicable)

All participants will receive a core 6-month weight loss intervention that includes evidence-based lessons, behavioral skills training, and daily self-monitoring of weight, dietary intake, and physical activity.

Study Design

The Nudge trial applies the Multiphase Optimization Strategy (MOST) framework and uses a microrandomized trial design to test the effects of 7 types of behavior change technique (BCT) messages on achievement of daily weight-related goals among 201 young adults. All participants will receive a 6-month behavioral weight loss intervention using our Nudge mobile app, which includes evidence-based weekly lessons, tailored feedback, self-monitoring, and daily BCT messages. Participants will receive a wireless scale, activity tracker, and track “red” foods (high-calorie foods) in the app and have 3 goals: weigh daily, a daily active minutes goal that gradually increases if met, and a daily red foods limit. At 3 decision points per day, participants will be microrandomized to receive or not receive 1 of 7 types of BCT messages. The outcome to be tested is the effect of BCT messages on achievement of same-day goal achievement (weighing, active minutes goal, red food limit). Assessments of the primary outcomes will occur daily, with assessments of secondary outcomes at 0, 3 and 6 months.

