- *Sedentary Activity* at baseline, 3, and 6 months will be assessed with the Sedentary Behavior Questionnaire from the EARLY trials (Rosenberg et al., 2010; Lytle et al., 2014).

Psychosocial measures

- *Self-efficacy for eating*, measured using the Weight Efficacy Lifestyle Questionnaire (WEL-Q; 20 items).³⁵
- *Self-efficacy for exercise*, measured using the 12-item Self Efficacy and Exercise Habits Survey.³⁶
- *Self-regulation for exercise*, measured with the 10-item Exercise Goal-Setting Scale and the 10-item Exercise Planning and Scheduling Scale.³⁷
- *Motivation for making changes in diet* (15 items) *and exercise* (15 items), measured using the respective Treatment Self-regulation Questionnaires.³⁸
- *Perceived competence for diet* (4 items) *and exercise* (4 items).³⁹
- *Health-related quality of life*, measured using the CDC Healthy Days measure (CDC 1993).
- *Depressive symptoms*, measured using the Center for Epidemiological Studies Depression Scale (CES-D).⁴⁰

- *Weight control strategies*, measured with the Weight Control Strategies Scale (WCSS; 30 items).⁴¹
- *Hunger, restraint, disinhibition* measured using the Three Factor Eating Questionnaire (TFEQ; 51 items).⁴²
- *Perceived stress*, measured using the Perceived Stress Scale (PSS; 10 items).⁴³
- *Binge eating* measured using the revised Questionnaire on Eating and Weight Patterns (QEWP-5).⁴⁴
- *Social comparison orientation* measured using the Iowa-Netherlands Comparison Orientation Measure (INCOM; 11 items).⁴⁵
- *Weight-related information avoidance* (10 items).⁴⁶
- *Relatedness* measured with a scale adapted from Basic Need Satisfaction at Work Scale (3 items).^{47,48}
- *Message relevance* measured using 2 items from our previous work,⁴⁹ which was adapted from previous studies.^{50,51}

Other measures

We will assess several supporting measures, including sociodemographic characteristics, medical events, and medication use. Program engagement (app views, lessons accessed, feedback messages viewed, goals set or modified), process, and adherence measures (self-weighing, activity tracking, red food tracking, daily goal achievement) will be collected throughout the study period and used to calculate behavioral adherence in the prior 7 days and streaks and lapses in goal achievement. Program acceptability and satisfaction will be assessed using post-intervention program evaluation questions and in post-intervention semi-structured interviews after 6 months.

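### Because unworn tracker days count as missed active-minutes goals, time trends (Aim 2) and moderation (Aim 3) on that outcome can reflect tracker wear rather than activity, by an amount that depends on an unstated link function

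*Combined protocol and SAP*

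**What the plan says.** Section 3 (Primary Proximal Outcome Measures) makes the active-minutes outcome dichotomous, and "days with no tracker wear are counted as not meeting the goal".

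Section 4 (Statistical Analysis Plan) then uses this outcome in two interaction analyses:

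- **Aim 2.** The model is extended by "including linear and quadratic main effects of time and interaction terms, between an indicator of day in the program and treatment assignment", in order "to test whether the treatment effect changes over time".
- **Aim 3.** The primary moderators are 7-day histories at the time of randomization: "achievement of weight-related behavioral goals, streaks and lapses in self-monitoring, weight change, previous BCT messages received".

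Two places bear on whether tracker wear belongs to self-monitoring. The synopsis describes the core program as including "daily self-monitoring of weight, dietary intake, and physical activity". Section 3 (Other measures) says that "adherence measures (self-weighing, activity tracking, red food tracking, daily goal achievement) will be collected throughout the study period"; the same sentence goes on to say that these measures feed 7-day adherence and streaks and lapses in *goal achievement*.

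The primary analysis is a GEE with an independence working correlation. No link function or effect scale is given. The one named sensitivity analysis (Section 4, Sample Size and Power) separates completers from dropouts. Nothing separates tracker wear from activity among participants who stay enrolled.

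**The concern.** On an unworn day the tracker sees no activity, and the outcome is zero whatever the participant did. The same non-wear also enters the Aim 3 moderators. Under the scoring rule an unworn day is itself a missed goal, so the 7-day goal-achievement history carries it directly. Lapses in self-monitoring plausibly carry it too. If recent non-wear predicts non-wear today, the moderator partly predicts whether the outcome can be observed at all. Program day does the same if wear declines over the 168 days.

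Section 1 (Study Objectives) says that the findings will shape an optimized intervention: which messages to send, when, and in which contexts. The trial could report that activity messages fade, or fail during lapses, when only measurement coverage fell. It could also report that they work best during lapses when they only prompted people to put the tracker on.

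**Working it through.** **The plan's own figure.** 168 × 0.83 + 84 × 0.17 = 153.72, rounded to 154 usable days; 201 × 154 = 30,954 person-days. This reproduces the plan and is the sample size in step 2.

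**Assumptions.** The documents give no wear or goal-attainment rates. I take attainment on worn days as 40% without and 45% with a message, at all times and in everyone. The standardized effect is 0.05 / √[(0.40 × 0.60 + 0.45 × 0.55) / 2] = 0.10, inside the plan's assumed range of 0.03 to 0.15.

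**Step 1. Messages change activity but not wear.** Recorded rate = w × p, where w is the share of days worn and p the attainment on worn days. The recorded difference is w × (0.45 − 0.40).

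| Wear w | No message | Message | Difference (points) | Log odds ratio | Risk ratio |
|---|---|---|---|---|---|
| 100% | 40.0% | 45.0% | 5.0 | 0.205 | 1.125 |
| 95% | 38.0% | 42.75% | 4.75 | 0.197 | 1.125 |
| 60% | 24.0% | 27.0% | 3.0 | 0.158 | 1.125 |
| 20% | 8.0% | 9.0% | 1.0 | 0.129 | 1.125 |

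The effect on activity is the same in every row. The difference shrinks in proportion to wear, the log odds ratio shrinks less, and the risk ratio does not change.

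**Step 2. How often a false lapse interaction is flagged on the difference scale.** Assume lapses on 30% of days, two-sided 5%, and independent observations. With wear of 95% outside and 50% inside a lapse, the false interaction is (0.95 − 0.50) × 0.05 = 0.0225.

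- Variance outside a lapse: (0.38 × 0.62 + 0.4275 × 0.5725) / (30,954 × 0.7 / 2) = 0.0000443.
- Variance inside: (0.20 × 0.80 + 0.225 × 0.775) / (30,954 × 0.3 / 2) = 0.0000720.
- Standard error 0.0108, z = 2.09, probability of flagging about 55% (23% with one third of the person-days).

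With wear of 90% against 70%, the interaction is 0.010, the standard error 0.01155 and z = 0.87. The flag rate is about 14%, or 8% with one third of the person-days.

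**Step 3. Time trend on the difference scale.** I simulated 400 trials per setting (201 × 154, linear model, cluster-robust errors). When wear fell from 95% to 50%, the false slope was −0.022 over the program and was flagged in 24%. When wear fell to 70%, it was flagged in 9.5%. With flat wear, flag rates were 4% to 7%.

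**Step 4. Linear against logistic.** Two harsher simulations (201 × 168, constant effect on worn days) compared the links:

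| Wear outside / inside a lapse | Linear: lapse | Linear: time | Logistic: lapse | Logistic: time |
|---|---|---|---|---|
| 88% / 31% | 87% | 29% | 12% | 6% |
| 90% / 20% | 97% | 21% | 16% | 6% |

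The second also tested the 7-day goal-achievement moderator, which was flagged in 82% (linear) and 30% (logistic).

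**Step 5. Messages change wear but not activity.** Suppose a message prompts wear on 10% of otherwise unworn days, and 40% of worn days meet the goal. The apparent effect is 0.40 × 0.10 × (1 − w): 0.2 points at 95% wear, 1.6 at 60% and 3.2 at 20%. The risk ratio is [w + 0.10 × (1 − w)] / w, which is 1.005, 1.067 and 1.40. No link removes this, and it is largest where wear is lowest.

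**Step 6. Does restricting by earlier wear help?** One simulation used one randomization per day, wear falling from about 92% to 58%, and a lapse set as three or more unworn days in seven. On all points, linear scale, a constant 5-point effect appeared as 4.2 points outside a lapse and 2.1 inside. Keeping only decision points with wear already recorded that day (about 72% of them) gave 5.0 and 4.8. In the wear-prompting scenario the restricted effects were 0 and 0. Lapse rejection in the restricted analysis was 9% and 5% in the two scenarios.

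**The case against.** The strongest reply is that the stated outcome is goal achievement, not latent activity. The non-wear rule is disclosed, and self-monitoring is part of the program. A smaller effect on *tracked and met* during lapses is then a true and usable finding. This stands, and it is why the outcome need not change for Aim 1. It does not say whether the smaller effect comes from less wear or less response, and those call for different designs of the next intervention.

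A reader might infer more than the documents support:

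- **That the Aim 2 and Aim 3 tests will usually give false positives.** High rejection rates appear only on a linear scale with large assumed wear contrasts. The plan names no link. With a logistic link the time result is near nominal and the lapse result modest. With a log link the first mechanism disappears. Multiplicity correction would lower rejection rates further, though it would not move the estimates.
- **That the plan defines self-monitoring lapses to include non-wear.** It does not. The synopsis counts activity as self-monitored, but Section 3 ties activity tracking to lapses in goal achievement. Inclusion is a reasonable inference. A definition spanning all three behaviors could have a weaker link to same-day wear.
- **That wear will decline, or that messages prompt it.** The documents quantify neither.

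Two objections to the remedy also stand. Restricting to wear earlier the same day needs time-stamped wear data, which the documents do not confirm. And requiring a significant result in the smaller subset, which holds few lapsed days, would mislabel real moderation.

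**Conclusion.** The point holds as a matter of interpretation in Aims 2 and 3. It is not a flaw in the Aim 1 outcome. On the active-minutes outcome, moderation by 7-day goal achievement or by self-monitoring lapses can reflect tracker wear, and so can a time trend if wear declines.

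The size rests on assumed rates and on the scale: material on the difference scale when wear differs widely between contexts, small when it differs modestly, smaller on the log-odds scale, and absent on a log link if messages do not affect wear. Without a message effect on activity or on wear there is no distortion. The Aim 3 case is stronger than the Aim 2 case. Wear prompting is the one mechanism that survives every link. Since the plan leaves the link open, whether moderation appears could turn on a choice not yet made.

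**What to change.** For the active-minutes outcome in Aims 2 and 3:

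1. State the link and effect scale of these models, and whether tracker non-wear enters the lapse moderator.
2. Fit the same time and moderator models to same-day tracker wear (yes/no) as a companion outcome.
3. As a sensitivity analysis, repeat the active-minutes models on decision points where wear was already recorded that day before randomization, if time-stamped wear data exist. Otherwise use days that follow a worn day. Both conditions are fixed before randomization, so the randomized comparison is kept; the second is the weaker restriction. Selecting on wear over the whole day would not be safe, because messages may change it.
4. Report interaction estimates and confidence intervals from the main, wear and restricted models side by side. Describe fading or lapse moderation as a change in *tracked and met* that may reflect wear, unless the restricted estimates are similar. Do not require significance in the restricted subset.

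Keep the current outcome for the Aim 1 test. The cost is a few sentences and a few extra model fits. The restricted analysis has fewer decision points, especially at the first one of the day if same-day wear is used, contains few lapsed days, and speaks only to days when the tracker is in use.
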